4.8. PHARMACOKINETIC AND PHARMACODYNAMIC ANALYSES

Non-linear mixed effects modelling will be used to analyze the sparse sampling dose-concentration-time data of prasinezumab including investigation of the influence of potential covariates on pharmacokinetic parameters.

Graphical exploration of the relationship between prasinezumab concentrations and MDS-UPDRS Total Score (sum of Parts I, II and III), other selected clinical endpoints, biomarkers and safety endpoints will be performed. If indicated by such exploration, more formal analyses of the PK/PD relationship using non-linear mixed effects modelling method will be undertaken. A previously developed disease model of the PPMI MDS-UPDRS total Score (sum of Parts I, II, and III) may be used to explore potential disease-modifying effect of prasinezumab and investigate potential covariates.

For the investigation of the drug effect, classical hierarchical PK/PD models will be tested. The possibility of a delay between the time-course of exposure and effects will be investigated using indirect pharmacodynamic models or using an effect compartment.

Details of the modelling analyses will be described in a Modelling and Simulation Analysis Plan. The results will be reported in a document separate from the clinical study report.

4.9. SAFETY ANALYSES

All safety analyses will be based on the safety analysis population, defined in Section 4.1.4. Safety will be assessed through the summary of adverse events, laboratory test results (hematology and serum chemistry), ECG findings, and vital signs. Safety summaries for the 52-week period in Part 1 will include outcomes as described in Section 2.6.

The incidence of antibodies against prasinezumab (ADAs) will be summarized using the immunogenicity population (Section 4.1.5).

4.9.1. Exposure of Study Medication

The study drug product was provided in vials (500 mg/10 mL) and administered IV after dilution in 250 mL 0.9% NaCl bags. The qualified individual (unblinded study pharmacist) responsible for dispensing the study drug at the site prepared the correct dose according to the randomization schedule provided by IxRS. The actual number of vials used to prepare each infusion was entered in IxRS. For each infusion the following are defined:

- The actual prepared dose is equal to the actual number of vials times 500mg.
- The actual received dose is equal to:
 - The actual prepared dose, if the infusion was not modified (infusion modified is equal to “No”)
 - The actual prepared dose × min (sum of volume administered at the same visit (from eCRF), 250)/ 250, if the infusion has been modified (infusion modified is equal to “Yes”)

4.9.2. Adverse Events

Verbatim descriptions of treatment-emergent adverse events will be coded using the latest version of MedDRA in effect at the time of database freeze. A treatment-emergent adverse event is defined as any new adverse event or any worsening of an existing condition with an onset date on or after the first study drug administration date.

Summaries of treatment-emergent events will be provided for each of the following categories:

- Incidence of adverse events
- Incidence of adverse events by intensity
- Incidence of adverse events by relationship to study medication
- Incidence of serious adverse events
- Incidence of adverse events leading to discontinuation of study treatment
- Incidence of adverse events of special interest
- Incidence of infusion related reactions

- C-SSR will be reported by visit

4.9.3. Laboratory Data

All clinical laboratory data will be stored on the database in the units in which they were reported. Participant listings and summary statistics at each assessment time will be presented using the International System of Units (SI units; *Système International d'Unités*). Laboratory data not reported in SI units will be converted to SI units before processing.

Descriptive summaries of laboratory test values will be presented by individual listings with flagging of values outside the normal ranges. Incidence of laboratory abnormalities (including hematology, clinical chemistry, coagulation, and urinalysis parameters) and incidence of BP abnormalities will be presented in summary tables by treatment arms.

Samples collected during Grade 3 and more severe IRRs will be analysed for tryptase, cytokine panel, C3a, C5a and their values will be presented by individual listings with flagging of values outside the normal ranges.

Standard Reference Ranges and Transformation of Data

Roche standard reference ranges, rather than the reference ranges of the investigator, will be used for all parameters. For most parameters, the measured laboratory test result will be assessed directly using the Roche standard reference range. Certain laboratory parameters will be transformed to Roche's standard reference ranges.

A transformation will be performed on certain laboratory tests that lack sufficiently common procedures and have a wide range of investigator ranges, e.g., enzyme tests that include AST, ALT, and alkaline phosphatase and total bilirubin. Since the standard reference ranges for these parameters have a lower limit of zero, only the upper limits of the ranges will be used in transforming the data.

Definition of Laboratory Abnormalities

For all laboratory parameters included, there exists a Roche predefined standard reference range. Laboratory values falling outside this standard reference range will be labeled "H" for high or "L" for low in patient listings of laboratory data.

In addition to the standard reference range, a marked reference range has been predefined by Roche for each laboratory parameter. The marked reference range is broader than the standard reference range. Values falling outside the marked reference range that also represent a defined change from baseline will be considered marked laboratory abnormalities (i.e., potentially clinically relevant). If a baseline value is not available for a patient, the midpoint of the standard reference range will be used as the Patient's baseline value for the purposes of determining marked laboratory abnormalities. Marked laboratory abnormalities will be labeled in the patient listings as "HH" for very high or "LL" for very low.

4.9.4. Vital Signs

Vital signs data will be presented by individual listings with flagging of values outside the normal ranges (Table 7) and flagging of marked abnormalities. In addition, tabular summaries will be used, as appropriate.

Orthostatic blood pressure and heart rate, together with its incidence of abnormal values will also be reported. Orthostatic hypotension is defined as a sustained reduction of systolic blood pressure of at least 20 mmHg or diastolic blood pressure of 10 mmHg within 3 min of standing (Freeman et al. 2011).

Postural orthostatic tachycardia is defined as a heart rate >120 beats/min (bpm) on standing or an increase in heart rate by > 30 bpm from a resting heart rate without clinically significant orthostatic hypotension (Argawal et al., 2007; Freeman et al., 2011).

Table 7. Vital sign normal ranges.

Parameters	Position	Low	High
Pulse Rate (bpm)	If supine is not available use semi-supine	50	99
SBP (mmHg)	If supine is not available use semi-supine	90	140
DBP (mmHg)	If supine is not available use semi-supine	60	90
Temperature (°C)		36.5	37.3
Respiration Rate (breaths per minute)	If supine is not available use semi-supine	12	25

Sitting values will be ignored.

4.9.5. ECG Data Analysis

ECG data will be presented by individual listings (each individual triplicate result will be listed) with flagging of values outside the normal ranges (Table 8) and flagging of marked abnormalities. If the overall interpretation for an ECG is normal, specific flagged abnormalities will not be listed. ECG results with a technical quality abnormal finding will be listed.

In addition, tabular summaries will be used, as appropriate. Incidence of ECG abnormalities (including changes from baseline) will be reported. The relationship between QTcF prolongation and the serum concentration of prasinezumab may be investigated in an exploratory manner. If positive dose-response trends are observed with prasinezumab in these analyses, concentration-QT modeling may be conducted with data pooled across studies PRX002-CL002 and BP39529.

The number and percentage of subjects falling into the clinical signal categories for QT/QTc (≤ 450 , $450 <$ and ≤ 480 , $480 <$ and ≤ 500 , $500 <$) will be provided by treatment and time-point. Sex or age specific drug effects on QT are possible and will be investigated.

RR measurements on selected safety ECGs (i.e. Baseline/Day 1 (pre-dose), Week 52 and Week 104, or early termination), will be provided by Biotelemetry for an exploratory Heart Rate variability analysis. The standard deviation of the RR interval for the individual participant may be assessed as an exploratory endpoint.

Table 8. ECG normal ranges

Parameters	Method	Low	High
Heart Rate ECG (bpm)	12 LEAD TRIPLICATE	50	99
PQ(PR) (msec)	12 LEAD TRIPLICATE	110	200
QRS (msec)	12 LEAD TRIPLICATE	80	100
Mean RR interval (msec)	12 LEAD TRIPLICATE	926 (range 785-1160)	
SDNN (standard deviation of normal-to-normal intervals) (msec)	12 LEAD TRIPLICATE	50 (range 32-93)	

RR will be used for exploratory HR variability analysis

4.9.6. Immunogenicity Data Analysis

For the analysis, the following definitions based on Shankar et al. 2014 as well as a Sponsor's definition for ADA with neutralizing potential, will be used to describe prasinezumab patients' immunogenicity as follows:

ADA Negative Participants are defined as:

- Patients with ADA negative or missing data at baseline and all post-baseline samples are negative, OR
- Patients with ADA positive at baseline and no post baseline sample with a titre that it is at least ≥ 4 fold greater than the titre of the baseline sample (treatment unaffected).

ADA Positive Participants will be classified as:

- *Treatment induced*: patients with ADA negative or missing data at baseline, but develop an ADA response following study drug exposure. These patients will also be classified into:
 - *Persistent*: patients who have post-treatment ADA positive samples over 16 weeks or more or the last ADA timepoint is positive.
 - *Transient*: at least one post-treatment ADA positive sample AND has only one ADA positive sample or the time between the first and last ADA positive sample is less than 16 weeks AND the last ADA sample is negative

- *Treatment enhanced*: Patients with ADA positive at baseline and the titre of one or more post-baseline samples is at least ≥ 4 fold increase greater than the titre of the baseline sample.

The numbers and proportions of ADA-positive patients and ADA-negative patients at baseline (baseline prevalence) will be summarized by treatment group. For those who are ADA-positive, titers will be estimated as well as antibody subtype. In addition, the numbers and proportions of ADA-positive patients and ADA-negative patients at baseline (baseline prevalence) and after drug administration (post-baseline incidence) will be summarized for patients on active treatment only.

4.9.7. Concomitant Medications

The original terms recorded on the participants' eCRF by the Investigator for concomitant medications will be standardized by the Sponsor using the WHODrug dictionary.

Concomitant medications will be presented in summary tables and listings.

4.9.8. Other analyses

Incidence of MRI abnormalities (changes from baseline only) will be reported by visit. C-SSRS data will be reported in a shift analysis.

4.10. MISSING DATA

For the primary endpoint, the secondary endpoints of MDS-UPDRS Part III , CGI-I, and PGI-C, and all the exploratory PRO endpoints, assessments performed while on any symptomatic PD treatment started after randomization or after an increase in symptomatic PD treatment will not be included in the analysis. For the MDS-UPDRS missing values will be handled via the MMRM methodology. Missing items values for MDS-UPDRS are dealt with as described in section 4.7.2.1.

Data with missing visit and/or scheduled timepoint information (if relevant) will not be included in summary tables summarized by visit (and scheduled timepoint if relevant).

Missing data for PROs will be treated in line with license holder manuals

- Digital Biomarkers and patient-reported outcomes (Smartphone and wrist-worn wearable assessments):
 - Diary questions (patient reported outcome [PRO]).
 - Patient Assessment of Constipation symptoms (PAC-SYM) questionnaire (PRO).
 - Hospital Anxiety and Depression Scale (HADS) total score and sub-scales: anxiety (HADS-A), and depression (HADS-D) (PRO).
 - EQ-5D-5L questionnaire (PRO).
 - Sensor data collected during "Active Tests", assessing motor symptoms (upper and lower body movement, upper limb dexterity, voice/speech) and non-motor symptoms - including an electronic Symbol Digital Modalities Test (eSDMT) to measure attention and executive function.
 - Sensor data collected during "Passive Monitoring" assessing activity, movement and motor symptoms associated with routine daily living.
 - Sensor data collected during "In-Clinic Assessments", including the Timed Up and Go Test and selected items from the Berg Balance Scale.

- Serum and CSF biomarkers related to Parkinson's disease (CSF in consented patients only) including (but not limited to) plasma levels of NFL and CSF levels of total alpha-synuclein, ABeta₁₋₄₀, ABeta₁₋₄₂, p-tau and total tau, soluble TREM2, YKL40, and IL-6..
- Change from baseline in α -synuclein pathology in peripheral nerves.
- Change from baseline in DaT-SPECT in binding ratio values for: striatum, caudate and putamen (average, ipsilateral and contralateral), except for ipsilateral putamen which is a secondary endpoint.
- DTI MRI for mean diffusivity and fractional anisotropy in striatum, caudate and putamen (ipsilateral, contralateral and average).
- ASL MRI for cerebral blood flow in striatum, caudate and putamen (ipsilateral, contralateral and average).
- Time to start or change of co-medication for non-motor symptoms that may be related to PD (cognition, constipation, depression, anxiety, excessive day time sleep, nocturnal sleep, urogenital symptoms/sexual dysfunction).
- Start or change of co-medication for non-motor symptoms that may be related to imaging biomarkers (DAT Scan and ASL).
- Parkinson-related effects on the loss of autonomic tone as measured by heart rate variability.
- Time to increase in symptomatic PD treatment dose.
- Time to decrease in symptomatic PD treatment dose.
- Composite of Part 2 and Part 3 sub-items (PCOR motor score) including all of MDS-UPDRS Part II items and the following four items from Part III: item 1: speech, item 9: arising from chair, item 10: gait, Item 11: freezing of gait.
- Composite of Part 2 and Part 3 sub-items (pREDi motor score) including the following MDS-UPDRS items: arising from chair, body bradykinesia, dressing, eating tasks, finger tapping dominant side, gait (Part 3), hand movements dominant side, hand movements non-dominant side, leg agility dominant side, leg agility non-dominant side, postural tremor dominant side, pronation supination movement of hand dominant side, pronation supination movement of hand non-dominant side, rest tremor amplitude upper extremity dominant side, rigidity upper extremity dominant side, speech (Part 2), speech problems (Part 3), toe tapping dominant side, turning in bed, walking and balance (Part 2); where dominant is the most affected side and non-dominant is the least affected side.
- MDS-UPDRS Part IV at week 52 only in participants who started dopaminergic treatment (levodopa or dopamine agonist).
- Time to the first occurrence of either of the following:
 - ≥ 2 points from MDS-UPDRS (Part I), or
 - ≥ 2 point from MDS-UPDRS (Part II), or

- Start of dopaminergic PD treatment (levodopa or dopamine agonist)
- Time to the start symptomatic PD treatment
- Rank ANCOVA analysis for the absolute change from baseline in the following MDS-UPDRS endpoints: total score (sum of Parts I, II and III), Parts IA, Part IB, Part I total, Part II total, Part III total, and Part III subscores (rigidity, bradykinesia, resting tremor and axial symptoms).

Analysis of Exploratory Efficacy Endpoints

All exploratory endpoints described in Section 2.3.3 will be summarized using descriptive statistics. For PRO endpoints, assessment taken after the start of symptomatic PD treatment (as described in Section 4.3.1) will not be included in the analysis. If applicable, exploratory endpoints may be analyzed with the methods below and will include the covariates described in Section 4.7.1:

- Continuous endpoints *via* ANCOVA and/or MMRM.
- Time-to-event data via Kaplan-Meier plot and/or Cox proportional hazards model.
- Ordered categorical data (e.g., individual MDS-UPDRS items) via Wilcoxon rank sum test.
- Binary data (such as responder analyses) via logistic regression.

Item response theory (IRT) can permit a more precise analysis by integrating the whole available items information and increase the probability to detect changes due to a drug effect (Ueckert 2014). Therefore, IRT has the potential to increase the sensitivity for assessing effects using the composite endpoint MDS-UPDRS and to detect a drug effect acting on the disease progression.

A baseline IRT model was built to analyze the baseline data in *de novo* patients from the PPMI database (Buatois et al 2015, Buatois et al 2016, Gottipatti 2019). It will be updated by including the Phase 2 data and extended to a longitudinal model that describes the time courses of the motor, non-motor and tremor disability in patient treated with placebo or with prasinezumab using non-linear mixed effects modelling (i.e. NONMEM). The results of the IRT analysis will be reported in a document separate from the clinical study report.

The results of the IRT and MRI analyses will be reported in a document separate from the clinical study report.

The analysis of the endpoints of time to increase or decrease in symptomatic PD treatment dose will only be undertaken if there are at least 20% of patients who had an increase or decrease in symptomatic PD treatment dose.

The primary endpoint of total MDS-UPDRS (sum of Parts I, II, and III) will be reanalysed by pooling the data from the two treatment arms and compare it to placebo.

Analysis of Endpoints from the Digital Biomarker Assessments (Smartphone & Wrist-Worn Wearable)

Each participant received a preconfigured smartphone and wrist-worn wearable with installed software for the digital biomarker assessments. The endpoints described in this section are derived from the results of the smartphone & wrist-worn wearable.

A separate document will describe how the model for the digital PASADENA motor score is being constructed.

Digital Biomarker (dBm) Single Features – Remote Monitoring

The following selected features from the digital biomarker remote monitoring will be analysed in the way described below:

Test Name	Feature Name
Draw a Shape	Trace Celerity for Spiral
Speeded Tapping Test 1F-2B	Uptime standard deviation
Hand Turning Test	Maximum Hand Turn Speed
Free Speech Test	Average difference of MFCC2 between voice segments
Sustained Phonation Test	Voice Jitter
Postural Tremor Test	Mean Squared Energy
Rest Tremor Test	Mean Squared Energy
Static Balance Test	Sway
Five U-turn Test	Median Turn Speed
Symbol Digit Modalities Functional Test	Total Score
Passive Monitoring – Turning	Median Turn Speed
Passive Monitoring – Gestures	Median Turn Speed

Each feature will be first normalised. Feature values will be aggregated by average over reported window (Table 5). Feature values will be considered missing if less than 3 feature values exist in this interval. The same random coefficients model used for primary analysis will be used for analysis of the dBm features. Assessment taken after the start of symptomatic PD treatment (described in Section 4.3.1) will not be included in the analysis.

Absolute change in digital PASADENA motor score – Remote Monitoring

The digital PASADENA motor score will be mapped according to the time windows described in Table 5. An average of the dBm score will be calculated for each visit using all the scores that are mapped within a single reporting window. Assessment taken after the start of symptomatic PD treatment (as described in Sections 4.3.1) will not be included in the analysis. A random coefficients model will be used for the analysis of the

dBM. The model involves a random intercept and a slope for each subject. Within each participant, the model will incorporate an unstructured variance-covariance matrix for the random error terms. If the unstructured covariance matrix is non-estimable other covariance structures like heterogeneous compound symmetry would be used. Parameters will be estimated with the use of restricted maximum likelihood, and the Kenward-Roger method will be used for calculating the denominator degrees of freedom.

Percent change in digital PASADENA motor score - Remote Monitoring

Percent change in digital PASADENA motor score will be analyzed in the same way as the absolute change in digital PASADENA motor as described above

Digital PASADENA motor Score – In Clinic Assessments

The digital PASADENA motor score derived from in clinic assessments will be analysed as the one obtained from remote monitoring, the only difference will be that the average of the dBM score will be over the time windows described in Table 4

Digital Biomarker Single Features – In Clinic Assessments

Selected features from the digital biomarker in clinic assessments will be analysed in the same way as the features from the remote monitoring.

dBM ePROs: PAC-SYM, Hospital Anxiety and Depression Scale (HADS), EQ-5D-5L will be analysed via ANCOVA and/or random coefficients model.

Diary Questions

The diary contained four questions related to symptoms with categorical responses ranging from 1 (no symptoms) to 6 (severe symptoms), three questions related to difficulty with sleeping with four categorical responses 1 (not at all) to 4 (a lot), two questions related to bowel movement with binary responses (Yes or No), and one question related to the number of nights with problems with sleep with categorical responses (Never, 1 night, 2-3 nights, 4-5 nights, 6-7 nights). The diary also contained a Health Survey with 5 questions capturing the number of days the patient had health related problems.

Each one of the responses from the diary questions will be mapped according to the windows described in Table 5. For questions with more than two categories, categorical responses will be treated as continuous and an average during the reporting window will be used for analysis; a random intercept model will be used for the analysis. For the questions with binary responses a logistic regression will be applied. Responses from the Health Survey will be analysed with a random coefficients model.

Exploratory subgroup analyses

The following subgroup analyses are exploratory and might not be reported in the clinical study report.

The following subgroup analyses will be undertaken for the primary endpoint, change from baseline in total MDS-UPDRS (sum of Parts I, II and III) at Week 52. The subgroup analyses will also be undertaken in the following endpoints: MDS-UPDRS Part II, MDS-UPDRS Part III, and MDS-UPDRS sums of Part II and III, DaT-SPECT, dBM score, MoCA score and the composite time to event. The subgroup analyses will be undertaken in the same way described for the subgroups analyses in Section 4.7.5:

- Age at baseline (< 60 years vs. ≥ 60)
- Gender (male vs. female)
- Disease duration (<12 months vs. >12 months)
- Age at diagnosis of Parkinson's disease (< 60 years vs. ≥ 60)
- Nucleus basalis of Meynert at baseline (atrophy vs. no atrophy)
- MoCA total score: lower (<22) vs. higher (>22)
- GBA Mutation (positive vs negative). This subgroup analysis will only be done if there are 15% of patients from the overall population.
- Motor sub-phenotypes:
 - tremor vs. akinetic-rigid vs. intermediate
 - tremor vs. postural instability gait dysfunction vs. indeterminate

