## **Digital Biomarker Remote Monitoring**

Participants will be provided and trained on the devices during screening. During the study, participants will be instructed to conduct an “Active Test” every day *in Part 1 and Part 2, and as per SoA in Part 3*, at approximately the same time (ideally in the morning, after breakfast). The “Active Test” consists of a short, preconfigured sequence of tasks that assess motor symptoms (upper and lower body movements, upper limb dexterity, voice/speech) and non-motor symptoms (including an eSDMT for cognition). For “Passive Monitoring”, participants will be instructed to carry the smartphone and wear the wrist-worn wearable throughout the day as they go about their daily routine. Selected PROs will be administered on the smartphone to reduce the site visit burden.

Device sensor data will be recorded continuously, throughout the “Active Tests” and “Passive Monitoring”. Sound will only be recorded during selected “Active Test” tasks. Data are encrypted and uploaded to secure servers whenever the phone is connected to WIFI.

Participants are asked to charge the devices overnight. If participants have a WIFI network at home, they are encouraged to connect their smartphone to enable data transfer. If no WIFI network is available, the sensor data will be transferred during site visits or after the devices have been returned.

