## **Digital Biomarker In-Clinic Assessments**

*In Part 1 and Part 2*, participants are instructed to bring the smartphone and wearable to every clinic visit to check adherence and technical status of the devices. *In Part 1 and Part 2, participants will receive replacement device sets if they are defective. In Part 3, device sets may not be replaced if they are defective. In Part 3, participants are instructed to bring the sets to the visits with in-clinic digital biomarker assessments once a quarter.*

*In Part 1 and Part 2*, at selected clinic visits, participants will be asked to conduct the “Active Test” tasks and two additional in-clinic only assessments (selected items from the Berg Balance Scale and the Timed-Up and Go Test) under the supervision of a person trained on the digital biomarker approach. *In Part 3 participants will only perform the “Active Tests” at the specified in-clinic site visits.*

For participants who have started dopaminergic treatment (levodopa or dopamine agonist), the in-clinic assessments will be performed in a practically defined “Off” state

(i.e., no levodopa or dopamine agonist medication since the evening before). The in-clinic assessments will be repeated not earlier than one hour after receiving medication in clinic (“On” state).

The smartphone and wearable must be returned to the clinic in cases where the subject does not meet eligibility criteria, at the end of the study and upon early termination.

At the end of the study or at the time when the subject has completed the study, participants will be asked to complete a pen & paper satisfaction survey on how they experienced using the smartphone and wrist-based wearable during the study.

The full detailed digital biomarker is described in the ‘PD Digital Biomarker (Smartphone) Manual’.

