4.6. TIME WINDOWS

The analysis of data will be undertaken using time windows. As all the endpoints in the study are collected at different time frequencies, three different set of time windows will be applied depending on the endpoint. The analysis of all the endpoints collected every four weeks will be undertaken using the time windows described in Table 3. For the scales and questionnaires collected every eight weeks or more, Modified Hoehn & Yahr, MDS-UPDRS, CGI-I, PGI-C, MoCA, PDQ-39, SCOPA-AUT, SE-ADL, and PDSS-2, the time windows that will be used in the analysis are described in Table 4. All the endpoints collected with the remote device will be analysed with the windows described in Table 5.

The reporting windows will be applied to every single data point obtained for analyses regardless of the visit label used to collect the data, i.e. scheduled, unscheduled, or prior to start symptomatic treatment visits. If there are two or more visits mapped to exactly the same reporting window, then the following rules will be used to apply the data analysis flag to the assessment, i.e. the data flag used for the by visits reported as described in this SAP:

1. If neither of the visits are labelled as “Prior to start dopaminergic treatment visit” (as per protocol), flag the data from the last available visit.
2. If any visit is labelled as “Prior to start dopaminergic treatment visit” (as per protocol), then flag the data from this visit in the analysis.

Table 3. Windows for assessments collected every four weeks (vitals, physical examination, C-SSRS, ECG, ADAs, hematology, etc).

	Scheduled Week	Scheduled Day	Reporting window		
Part 1	1	1	≤ 1		
	1	2	2	to	4
	1	7	5	to	10
	2	14	11	to	20
	4	28	21	to	41
	8	56	42	to	69
	12	84	70	to	97
	16	112	98	to	125
	20	140	126	to	153
	24	168	154	to	181
	28	196	182	to	209
	32	224	210	to	237
	36	252	238	to	265
	40	280	266	to	293
	44	308	294	to	321
48	336	322	to	349	
52	364	350	to	Day before re-randomization to Part 2	

Table 4. Windows for assessments collected every 8 weeks or more

	Scheduled Week	Scheduled Day	Reporting window		
Part 1	1	1	≤ 1		
	8	56	2	to	83
	16	112	84	to	139
	24	168	140	to	195
	32	224	196	to	251
	40	280	252	to	307
	48	336	308	to	349
	52	364	350	to	Day before re-randomization to Part 2

Table 5. Windows for assessments collected in the remote device

	Scheduled Week	Scheduled Day	Reporting window		
Part 1	1	1	≤ 1		
	2	14	2	to	20
	4	28	21	to	34
	6	42	35	to	48
	8	56	49	to	62
	10	70	63	to	76
	12	84	77	to	90

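### Read literally, the minimum of three values per window leaves the exploratory in-clinic digital single-feature analysis with essentially no scheduled post-baseline data

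*SAP*

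**What the plan says.** SAP Appendix 1 sets the method for single features under remote monitoring. Each feature is normalised, then "Feature values will be aggregated by average over reported window (Table 5"), and then comes the completeness rule: "Feature values will be considered missing if less than 3 feature values exist in this interval". Assessments after the start of symptomatic PD treatment are left out, and a random coefficients model is fitted.

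The in-clinic single features get one sentence: "Selected features from the digital biomarker in clinic assessments will be analysed in the same way as the features from the remote monitoring". It gives neither a window nor a minimum count. The in-clinic motor score, dealt with just before it, does get an explicit departure from its remote counterpart: "the only difference will be that the average of the dBM score will be over the time windows described in Table 4". The motor score has no minimum of three in either setting.

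On frequency in Part 1, Protocol Section 4.6.1.9 says of the home tests that "participants will be instructed to conduct an “Active Test” every day", and of the supervised tests that "at selected clinic visits, participants will be asked to conduct" the Active Test tasks, plus balance and Timed Up and Go tests done only in clinic. SAP Table 4, used for the in-clinic motor score, is titled "Windows for assessments collected every 8 weeks or more".

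**The concern.** A minimum of three values per 14 days is sensible for a test done every day. It does not suit a test done once at a clinic visit. If a programmer applies the SAP as written, scheduled in-clinic sessions cannot meet the threshold and a planned exploratory analysis comes out empty. Features taken from the balance and Timed Up and Go tests would have no remote substitute, because those tests are done only in clinic.

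If the rule is instead dropped informally, the window and the minimum count become undocumented choices. They could be made after treatment codes have been released to the sponsor personnel analysing Part 1 (Protocol Section 4.3).

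**Working it through.** The plan gives no figure to reproduce. The check counts scheduled in-clinic days per reporting window and compares the count with three.

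Inputs:
- Table 5 (SAP Section 4.6): post-baseline windows are Days 2–20, then 14-day windows 21–34 to 343–356, then Day 357 to the day before re-randomization. That is 1 + (356 − 20)/14 + 1 = 1 + 24 + 1 = 26.
- Table 4 (SAP Section 4.6): seven post-baseline windows, 2–83, 84–139, 140–195, 196–251, 252–307, 308–349, and 350 onward.
- Visits (Protocol Appendix 1): dosing every 28 days from Day 28 to Day 364, each ±4 days. The first 90 US participants also attend on Days 7 and 14.
- Assumptions: one value per feature per session, and the last window ended at Day 395 (Week 56 is Day 392; 392 + 4 − 1 = 395). The Part 1 schedule row for in-clinic digital tests is not in the text available to me, so three schedules were tried.

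A dosing visit on Day 28k falls in the Table 5 window from 28k − 7 to 28k + 6 (the last is open-ended), so a shift of ±4 days never moves it into another window. Day 28, for example, can fall on Days 24–32, inside 21–34.

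| Windows | Assumed in-clinic schedule | Most values in any window | Windows reaching 3 (nominal days) |
|---|---|---|---|
| Table 5 | 8-weekly plus Week 52 | 1 | 0 of 26 |
| Table 5 | every 4-weekly dosing visit | 1 | 0 of 26 |
| Table 5 | 4-weekly plus US Days 7 and 14 | 2 (Days 2–20) | 0 of 26 |
| Table 4 | 8-weekly plus Week 52 | 1 | 0 of 7 |
| Table 4 | every 4-weekly dosing visit | 2 | 0 of 7 |
| Table 4 | 4-weekly plus US Days 7 and 14 | 4 (Days 2–83) | 1 of 7 |

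The ±4-day allowance changes nothing in the three Table 5 rows or in the 8-weekly Table 4 row. With 4-weekly testing and Table 4, any one of the first five windows could reach three, but only if the visit that nominally opens the next window came early (for instance the Day 84 visit on Days 80–83).

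By comparison, daily home testing gives up to 14 values in a 14-day window.

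The repeat in-clinic test in the On state adds nothing. It applies only to participants on dopaminergic treatment, and assessments after the start of symptomatic treatment are excluded.

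With a minimum of one value and Table 4 windows, the 8-weekly schedule gives 7 of 7 evaluable post-baseline windows.

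**The case against.** The literal reading is not the only one. The rule on missing values stands under the remote-monitoring heading and refers to a Table 5 interval, and SAP Section 4.6 assigns Table 5 to data collected with the remote device. Analysing in-clinic features like remote ones could mean only the same model and the same exclusion after symptomatic treatment, and the preceding paragraph already moves the in-clinic motor score to Table 4. An all-missing output would also be noticed at programming.

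This shows that the wording is ambiguous; it does not supply the missing rule. The in-clinic Active Test runs on the same devices, the Table 4 list in Section 4.6 does not name in-clinic digital tests, and the exception written for the motor score is not repeated for the single features. Even if Table 4 is assumed, nothing lifts the minimum of three.

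Other parts of the objection stand. The rule counts feature values, not visits, and the SAP does not say how many values one session yields. The exact in-clinic schedule is inferred. Unscheduled visits may include these tests at the investigator's discretion (Protocol Section 4.6.2.5), so clustered extra visits could occasionally bring a window to three. A reader might infer that every in-clinic value is bound to be lost; the documents do not support that.

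A reader might also infer that the supervised data are discarded altogether and that home testing loses its only check. That is not supported either. The in-clinic motor score keeps its own windows with no minimum, MDS-UPDRS Part III is unaffected, and no document calls the in-clinic features the only check.

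**Conclusion.** The point holds as a literal-reading defect in the SAP. Under Table 5, with one value per feature per session, no tested schedule brings any of the 26 post-baseline windows to three values, so the analysis would have essentially no scheduled post-baseline data. That result does not depend on the exact in-clinic schedule, from 8-weekly up to every dosing visit plus the US Day 7 and Day 14 visits. The further conclusion, that moving to Table 4 is not enough by itself, does depend on testing being about 8-weekly.

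The consequence is limited. Appendix 1 lists exploratory analyses that might not enter the clinical study report. It would be wrong to infer any effect on the primary, secondary or in-clinic motor-score analyses, since none of them uses this rule.

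**What to change.** In SAP Appendix 1, state that the minimum of three feature values applies to remote monitoring only. For in-clinic single features, specify the Table 4 windows, average the values available in each window as is done for the in-clinic motor score, and require at least one value. It would help to add how many values one in-clinic session yields per feature.

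The cost is a sentence or two in the appendix and a small programming change, with no new data. The downside is that a window value resting on a single session is noisier than an average of several.
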